All clusters in intervention arm will receive the GOS traps. A maximum of 21 traps will be set per apartment block, on every third floor. The traps will be monitored weekly and the abdomen of *Aedes* obtained will be tested for dengue virus using the NS1 antigen test kit. If positive search and destroy measures will be conducted by the community under the supervision of community leader and the health staff. To identify the mosquito which carries the virus, dengue NS1 antigen tests will be carried out from the head and thorax of the individual mosquitoes from positive pool of mosquitoes. For the control clusters, routine dengue control and surveillance will be carried out as per the current Ministry of Health control activity, where no traps will be set, and dengue control measure will be initiated when human cases are reported from the control group. Data collection will be conducted for 1 year and 6 months.

When a positive mosquito is obtained, flyers and banners will be distributed and hung to inform the residents of the presence of dengue transmission in the apartment block/apartment. Alternatively, the residents may also be approached house-to-house or an educational booth set up at strategic locations in the apartment to warn and educate the residents.

Phase III: Repeat of KAP questionnaire

The KAP questionnaire survey will be repeated 15 months after intervention in the intervention arm.

Phase IV: Statistical Analyses

Data of serologically confirmed dengue cases (by NS1 or IgM/IgG) from the eight residential blocks will be obtained from the Selangor State Health Department, Malaysia. It is mandatory for all hospitals and private practitioners to report cases to the Ministry of Health. The date of onset of case will be used for all data analyses.

For analysing the change in level of dengue KAP, the mean of the percentage score of the population for each domain (knowledge & attitude/practises) will be determined for the pre- and post-questionnaire. Then, paired t-test will be performed to determine the presence of significant changes in both means. A p-value of at most 0.05 indicates a significant change/improvement in the mean score (An increase in score percentage indicate a better outcome). Additionally, an individual percentage score of 80% and above indicates good knowledge/attitude/practice. Accordingly, chi-squared test will be used to determine the extent to which good knowledge is related to good attitudes/practises

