All statistical analyses will be done using weekly data and R programming language for statistical analysis (version 3.2.4) (30). The family of distributed lag non-linear models (DLNM), (*DLNM* package version 2.20), which can simultaneously analyse non-linear factor-response dependencies and delayed effects, and provides an estimate of the overall effect in the presence of delayed contributions will be utilised. For dengue cases and its relation to dengue-positive *Aedes* pool, the model to be used will be: `glm(case ~ cb.total_aedes + cb.ns1positive + ns(time, 3) + woy, family = quasipoisson, data)` where `woy` = week of the year. Both the *Ae. aegypti* / *Ae. albopictus* trapped per week and cases per week at each apartment will be analysed by generalised linear mixed model (GLMM). Zero inflation and Poisson distribution were incorporated in the analysis. Differences in numbers of *Ae. aegypti* and cases between blocks and between floors were tested with Tukey's contrasts at $P = 0.05$.

References

1. Gubler, D.J., and Clark, G.G. (1995). Dengue/dengue hemorrhagic fever: the emergence of a global health problem. *Emerg Infect Dis* 1, 55.
4. Faria NR, da Silva Azevedo RS, Kraemer MU, Souza R, Cunha MS, Hill SC, et al. (2016). Zika virus in the Americas: Early epidemiological and genetic findings. *Science* 352(6283):345-9.

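### The analysis plan specifies no intervention-versus-control comparison of dengue cases, although the trial randomises and is sized for that effect

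*Combined protocol and SAP*

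**What the plan says.** The intended comparison is clear. Sections 2 (Aim) and 3 (Objectives) set the new surveillance approach against usual Ministry of Health activity. Section 7, under the sample size for the intervention trial, assumes a 2% yearly dengue risk per housing unit, a 50% reduction, 80% power and alpha 0.05. It asks for 2855 units per arm and randomises eight apartments holding 7979 units.

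Phase II states that control clusters are ones "where no traps will be set", and that "Data collection will be conducted for 1 year and 6 months". Phase IV obtains notified confirmed cases for all eight residential blocks.

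Phase IV then says four things about analysing cases:

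- A distributed-lag model, introduced with "For dengue cases and its relation to dengue-positive" pools, is written as "glm(case ~ cb.total_aedes + cb.ns1positive + ns(time, 3) + woy, family = quasipoisson, data" (closing bracket omitted here).
- Weekly counts: "cases per week at each apartment will be analysed by generalised linear mixed model (GLMM" (closing bracket again omitted).
- Distribution: "Zero inflation and Poisson distribution were incorporated in the analysis".
- Contrasts: "cases between blocks and between floors were tested with" Tukey's method.

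The knowledge, attitude and practice (KAP) scores get a paired pre-post t-test, and Phase III says "The KAP questionnaire survey will be repeated 15 months after intervention in the intervention arm".

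**The concern.** A cluster-randomised trial needs a stated analysis of the effect it randomises. Here the sample size section poses a two-arm question about dengue cases and the analysis section does not answer it. No sentence on the analysis of cases mentions arm, intervention or control.

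Two things are at stake. The plan as written could be carried out in full without producing an effect estimate. The arm test that someone would then add is also open to choice once the data are known. With only eight randomised units, tests that each look reasonable have very different false-positive rates.

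**Working it through.** **Step 1. Does any planned analysis compare the arms on cases?**

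| Planned analysis | What it estimates | Arm comparison of cases? |
|---|---|---|
| Distributed-lag quasi-Poisson glm | Association of cases with trapped *Aedes*, NS1-positive pools, time and week of year | No. There is no arm term, and at apartment level the trap covariates do not exist in control clusters. Pooled into one weekly series, it still would not compare arms. |
| GLMM of weekly cases per apartment | Not stated: no fixed effects, random effects, offset or inference | Could carry one; none is stated |
| Tukey contrasts | Differences among blocks and among floors | No. If blocks are the apartments, there are 8 × 7 / 2 = 28 pairs, of which 4 × 4 = 16 cross arms under a 4:4 split. Each pair mixes the arm effect with apartment-to-apartment variation. |
| KAP paired t-test and chi-squared test | Change within the intervention arm; knowledge against attitude/practice | No, and not on cases |

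The count of stated intervention-versus-control estimates for cases is zero.

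**Step 2. The plan's own figure.** A two-sided comparison of 2% with 1% at 80% power needs 2319 units per arm, or 2515 with continuity correction, ignoring clustering. The stated 2855 does not reproduce from its stated inputs; the closest variant found is 85% power with continuity correction, 2849. That is a separate matter. What counts here is that the calculation is a two-arm comparison of dengue risk.

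**Step 3. How much the open choice matters.**

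From the document: 2% per unit-year, halved under the alternative; 7979 units; eight apartments; 18 months. Assumed: a 4:4 split, equal apartments (7979 / 8 ≈ 997 units), Poisson counts without zero inflation, log-normal apartment rates, and a between-apartment coefficient of variation (CV) from 0 to 0.5.

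Expected cases per apartment over 18 months: 997 × 0.02 × 1.5 = 29.9 (control) and 997 × 0.01 × 1.5 = 15.0 (intervention).

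Simulated type I error at nominal 5%, 18 months:

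| Arm test the plan leaves open | CV 0 | 0.1 | 0.25 | 0.4 | 0.5 |
|---|---|---|---|---|---|
| Weekly quasi-Poisson with arm, no apartment term | about 5% | 9% | 24% | 39% | 48% |
| GLMM with arm and apartment random effect, Wald z | 4.5% | 6.7% | 12.4% | 13.3% | 13.8% |
| Same GLMM, t on 6 df | 1.3% | 2.4% | 6.5% | 7.3% | 8.0% |
| t-test on eight apartment log rates | 4.8% to 5.1% throughout | | | | |

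Runs per cell: 10,000, 4,000, 4,000 and 40,000 in row order. The GLMM was fitted by maximum likelihood to apartment totals, which is adequate if season is common to all apartments.

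Hand check of the first row. With s² = ln(1 + CV²) and μ = 29.9, the null variance of the difference in log rates is (2/4)(1/μ + s²). A test ignoring apartment uses (2/4)(1/μ). At CV 0.25, s² = 0.0606 and 1/μ = 0.0334, so the variance ratio is (0.0334 + 0.0606) / 0.0334 = 2.81. The error rate is 2[1 − Φ(1.96/√2.81)] ≈ 24%.

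Hand check of the GLMM rows at high CV. Maximum likelihood divides the between-apartment sum of squares by 8, not 6. Wald z therefore rejects when |t on 6 df| exceeds 1.96√(6/8) = 1.70, which has probability 14%. With the 6-df critical value the cut-off is 2.447√(6/8) = 2.12, probability 7.8%.

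**Step 4. What a valid test could deliver.** t-test on log(cases + 0.5), true rate ratio 0.5:

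| | CV 0 | 0.1 | 0.25 | 0.4 | 0.5 |
|---|---|---|---|---|---|
| Power, 18 months of exposure | 96% | 92% | 69% | 44% | 34% |
| Power, 15 months of exposure | 92% | 87% | 65% | 43% | 33% |
| Typical 95% CI, 18 months | 0.35–0.72 | – | 0.29–0.87 | 0.24–1.05 | – |

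Power falls below 80% at a CV of about 0.19 (18 months) or 0.16 (15 months). The 15-month row is a sensitivity case only. That interval appears in Phase III as the timing of the repeat survey, and the exposure period to be counted for cases is not separately defined.

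**The case against.** The best reply is that the plan is underspecified, not empty. The sample size section gives an arm hypothesis on dengue risk, the Aim names the comparator, and a GLMM on cases from all eight blocks could hold an arm term. All of that is true, and it shows intent. It does not make a specification: where the plan does name contrasts for cases, it names blocks and floors.

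Four narrower points stand as qualifications.

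- The document uses both apartment and block. Reading the eight reported blocks as the eight randomised apartments is natural but should be confirmed.
- The sample size is built on the risk that a housing unit has dengue. A rate of cases per unit-year is a related but different outcome, because one household can have several cases.
- Every CV above zero is an assumption, and the simulated GLMM omits zero inflation. The figures show why the choice matters; they do not establish the omission, which is textual.
- The t-test is one sound choice among several.

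The KAP design is a separate issue and adds no weight here.

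**Conclusion.** The concern holds, and the plan is wrong as written on this point. It contains no intervention-versus-control estimand, model term, contrast or test for dengue cases, so the randomised effect has no prespecified estimate, interval or p-value. That conclusion comes from the text and needs no assumption.

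The size of the consequence is conditional on the assumptions in the working. At CVs of 0.25 to 0.5, arm tests the plan leaves open run from about 5% to 48% type I error. At CV 0 none exceeds about 5%. Section 2's statement that the hypothesis is judged by entomology surveys does not fill the gap: trap counts exist in one arm only, and no other between-arm entomological comparison is planned. This must be fixed before cases are compared by arm.

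**What to change.** Before any comparison of cases by arm, prespecify one primary analysis on all eight apartments that respects apartment randomisation and the small number of clusters.

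- **Suitable choice:** log((cases + 0.5) / unit-years) for each apartment, compared between arms by a pooled t-test on 6 df, and reported as a rate ratio with 95% CI.
- **Acceptable alternative or supportive analysis:** the planned GLMM with arm fixed, apartment random, offset log(units), seasonal terms and no mosquito covariates. State its small-sample inference (not Wald z) and check it by simulation at eight clusters; t on 6 df alone still gave 6.5% to 8.0% at CVs of 0.25 to 0.5.
- **State also:** apartments per arm, the exposure period counted, whether the outcome is cases or affected units, and that the reporting blocks are the randomised apartments.
- **Keep** the distributed-lag model as a secondary association analysis in trapped apartments, and do not read block or floor contrasts as a test of the intervention.
- **Reconcile** the entomological assessment in sections 2 and 3 with the case outcome used for sizing.

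The cost is SAP text and a short analysis. If blocks and apartments coincide, no new case data are needed, but units per apartment must be recorded. The downside is wider intervals and lower power than a unit-level analysis, as Step 4 of the working shows. An unequal split costs a little more: with five intervention and three control apartments, 18-month power is 93%, 88%, 64%, 41% and 31% across the same CVs.

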Subsequent to the above-mentioned phase 1 study, a prospective longitudinal phase 2 study was initiated to evaluate the use of Gravid Ovipositing Sticky (GOS) trap and the NS1 testing system for surveillance of dengue virus transmission in urban Malaysia over a two-year period. The findings showed that dengue cases would occur lag one week after infected mosquitoes are obtained and will peak at lag of 2 to 3 weeks (30). These results showed that this proactive strategy is beneficial for dengue vector surveillance programme. The usage of the GOS trap which is simple to setup, cost effective (below USD 1 per trap) and environment friendly (i.e. use recyclable plastic materials) to capture *Ae. aegypti* followed by a rapid method of detecting of dengue virus using the NS1 dengue antigen kit has shown promising results. Control measures could be initiated when positive mosquitoes are detected, for example activity such as search and destroy breeding containers. This innovative usage of GOS trap coupled with NS1 detection in mosquito provides a comprehensive early warning and surveillance system that has the predictive capability for epidemic dengue.

6. Relevance to Government Policy, if any

This cluster randomised trial is expected to provide robust estimates of the intervention effects. A rigorous evaluation of these vector control interventions is vital to the development of an evidence-based control strategy and to help direct government resources in the right direction to reduce dengue epidemics.

7. Methodology

This is a community-based study assessing the knowledge, awareness and practice on dengue infection and its prevention. We choose PJU10 because it is the dengue 'hotspot' area according to local health council. We have identified a low-cost housing area with population of approximately 48700 people.

Sample size calculation:

Sample size for intervention trial:

To test for effectiveness of intervention in reducing dengue cases, on average, each housing unit will have 2% risk of dengue per year. A sample of 5710 unit (2855 per arm) will be required to achieve 80% power at alpha of 0.05 with the assumption of reduction in 50% of risk at the end of intervention. Eight apartments with 7979 residential units will be selected and randomised into intervention and control. Apartment will be the item of randomisation.

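### No week-to-week correlation term is stated for the weekly GLMM, so block contrasts can exceed their 0.05 level if runs of high or low weeks are specific to a block

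*Combined protocol and SAP*

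**What the plan says.** All of this is in section 7, Methodology, unless noted.

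- **Time unit and length.** "All statistical analyses will be done using weekly data" (Phase IV), and "Data collection will be conducted for 1 year and 6 months" (Phase II). That is about 78 weeks per series.
- **Model.** Weekly catches of each Aedes species and "cases per week at each apartment will be analysed by generalised linear mixed model (GLMM". The only structure given is "Zero inflation and Poisson distribution were incorporated in the analysis".
- **Tests.** Differences in numbers of Ae. aegypti and "cases between blocks and between floors were tested with Tukey's contrasts", at the 0.05 level.
- **Time terms.** These are written only for the separate distributed lag model, whose formula contains "cb.total_aedes + cb.ns1positive + ns(time, 3) + woy, family = quasipoisson". No formula is given for the GLMM: no random effects, week or season term, autoregressive structure or robust variance.
- **Background.** The Literature Review reports from the phase 2 study that "dengue cases would occur lag one week after infected mosquitoes are obtained and will peak at lag of 2 to 3 weeks".

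**The concern.** Weekly counts from one block are repeated measurements of the same place. Outbreaks last more than a week, and traps are read weekly. The response is also local. A positive mosquito in a trapped block sets off a community clean-up and notices to that block's residents, and in control clusters measures start when cases are reported there. Some runs of high or low weeks are therefore likely to belong to one block.

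A model that treats such weeks as independent counts too much information. Correcting overdispersion repairs the variance of a single week but not the correlation between weeks. A random intercept for block does not help either, because it is constant over time. A week effect common to all blocks removes only the shared part.

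At stake is whether a chance run in one block is reported as a real block difference in vectors or dengue. An analyst could fit exactly the stated structure, comply with the plan, and obtain standard errors that are too small.

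**Working it through.** **Inputs from the plan.** About 78 weeks; Tukey contrasts at 0.05; 8 apartments with 7979 units; 2% risk per unit per year; no traps in control clusters. Expected cases with no intervention effect: 7979 × 0.02 × 1.5 = 239, and 239 / (8 × 78) = 0.38 per apartment-week.

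**Assumptions, because the documents are silent.** Week-to-week correlation rho; log-scale SD of the weekly rate (0.5 for catches, 0.8 for cases); mean catch of 10 per block-week; 4 trapped blocks (equal split, one block per apartment); and the share of the weekly signal common to all blocks.

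**Step 1. The plan's own figure.** The 0.05 is a chosen threshold. With independent weeks (rho = 0) the studentized-range calculation returns a family-wise error of 0.050.

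**Step 2. Analytic effect of residual correlation.** For residual correlation rho specific to each block and T = 78, the variance inflation is VIF = 1 + 2 Σ (1 − k/T) rho^k. The family-wise error is 1 − F_range(q_0.95 / √VIF).

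| Residual rho | VIF | √VIF | 78 / VIF (weeks) | Error, 4 blocks | Error, 8 blocks |
|---|---|---|---|---|---|
| 0.3 | 1.84 | 1.36 | 42 | 0.23 | 0.33 |
| 0.5 | 2.95 | 1.72 | 26 | 0.44 | 0.64 |
| 0.7 | 5.47 | 2.34 | 14 | 0.69 | 0.90 |

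**Step 3. Poisson noise dilutes the correlation.** In the simulations rho applies to the underlying log rate. The observed lag-1 correlation is m(exp(s²·rho) − 1) / [1 + m(exp(s²) − 1)], with m the mean and s the log SD. At rho = 0.5:

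- catches (m = 10, s = 0.5): 10 × 0.133 / (1 + 10 × 0.284) = 0.35;
- cases (m = 0.384, s = 0.8): 0.384 × 0.377 / (1 + 0.384 × 0.896) = 0.11.

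So the errors below are smaller than in step 2, above all for cases.

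**Step 4. Simulation with no true difference.** Poisson counts with a log-normal AR(1) rate, quasi-Poisson standard errors (overdispersion already handled), Tukey contrasts. Family-wise error at rho 0.3 / 0.5 / 0.7:

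| Weekly signal | Catches, 4 blocks | Cases, 8 apartments |
|---|---|---|
| Wholly block-specific | 17% / 33% / 61% | 7% / 13% / 27% |
| Half shared, no week effect fitted | 4% / 12% / 37% | 3% / 5% / 13% |
| Wholly shared | about 1% or less | about 1% |

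Repeat runs agree to within about 4 percentage points.

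**Step 5. Does a common week effect suffice?** No. With half the signal shared and a week effect fitted (4 blocks, mean 5, log SD 0.7), the error for catches is 21% / 36% / 59%. The half-shared row in step 4 is low partly because the shared variation enlarges the standard errors.

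**Step 6. Floors.** Assumed: 4 blocks, 6 floors, mean 2 per floor-week, log SD 0.5, block effects fitted. If the signal is block-wide the error is 0.3% to 0.8%. If 80% of it is block-wide, the error is 2% / 3% / 6% at rho 0.3 / 0.5 / 0.7 and 14% at 0.8. If it is wholly floor-specific, the error is 23% at 0.5 and 45% at 0.7.

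**Step 7. Aggregation.** With six 13-week totals per block (6 × 13 = 78), quasi-Poisson variance and degrees of freedom from the block-periods, the block contrasts have an error of about 3% to 12%, even with a wholly block-specific signal.

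**The case against.** - **Silence is not absence.** A reader might infer that the GLMM lacks a serial term. The plan gives no GLMM formula, and a GLMM can carry block-by-period or autoregressive effects. Only "not stated" is supported. This stands.
- **The error may be small.** All apartments lie in one locality, so shared season and weather are plausible, and correlation common to all blocks cancels in block contrasts. A reader might infer that false block differences will certainly be frequent. The documents give no correlation, catch variance or shared fraction, so the true rate could lie below or well above 5%. This stands, but the local response described in Phase II gives reason to expect some block-specific part.
- **The cited lag is indirect.** The Literature Review lag runs from infected mosquitoes to human cases. It links two series. It is not autocorrelation within either, and says nothing about total catches. This stands; the argument rests on local outbreaks and local responses.
- **Floors and cases are not like catches.** A reader might extend the catch figures to both. A signal shared by the floors of one block largely cancels in floor contrasts. At 0.38 cases per apartment-week the inflation can be negligible: with log SD 0.5 it is 5% to 6% at rho 0.3 to 0.5, even if block-specific.
- **Plain Poisson may be the larger fault.** Without overdispersion handling, the error for catches (mean 5, log SD 0.7, block-specific) is 73% to 92% at rho 0.3 to 0.7. True, but step 4 shows that curing it leaves this problem in place.
- **The trial's conclusion is not at risk from this.** A reader might infer that the test of the intervention is invalid. Traps exist in one arm only, and no arm term is stated for the GLMM. The contrasts concern blocks and floors, not the randomised comparison.

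**Conclusion.** The point holds in conditional form. The plan tests block differences on about 78 weekly counts per block and states no term for correlation between those weeks. Where that correlation is partly block-specific, the block contrasts can exceed 0.05 even with overdispersion corrected. For catches the error is several times nominal at moderate correlation if the signal is wholly block-specific, around or above nominal if half is shared and no week effect is fitted, and below nominal if all is shared. For cases it runs from about 1% to 27% under the settings used. Floor contrasts are affected only so far as runs are floor-specific. All sizes rest on assumed correlation, log SD, catch mean and number of blocks. More blocks would mean more contrasts and greater inflation, as the 8-block column of step 2 shows. This is a cheap improvement to a secondary analysis, not a defect in the randomised arm comparison.

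**What to change.** In Phase IV, write out the GLMM and choose one of two routes:

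1. Add a week effect shared by all blocks and a first-order autoregressive week effect within each block (within each floor for the floor contrasts).
2. Base the block contrasts on 13-week totals, with quasi-Poisson variance and degrees of freedom taken from the number of block-periods: 4 × 6 = 24 for catches under the equal-split assumption, 8 × 6 = 48 for cases, each less the number of block means.

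Under either route, report the residual autocorrelation of the weekly model.

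Route 2 is simpler but leaves some inflation (error up to about 12% for catches in simulation). Route 1 addresses the cause directly, though its error rate was not simulated here. The cost is a sentence or two in the plan, slightly more modelling and wider intervals. If the correlation proves negligible, little is lost.

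### The analysis takes weekly case and mosquito counts as responses and states no exposure term for housing units or traps. The cost runs from negligible to serious, depending on size differences that the protocol does not report.

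*Combined protocol and SAP*

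**What the plan says.** **Responses.** Under Phase IV: Statistical Analyses, weekly catches of the two *Aedes* species and "cases per week at each apartment will be analysed by generalised linear mixed model (GLMM"). On the distribution, the plan adds: "Zero inflation and Poisson distribution were incorporated in the analysis". No link, fixed effects, random effects or offset are given.

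**Contrasts.** The same paragraph says that differences in numbers of *Ae. aegypti* and "cases between blocks and between floors were tested with Tukey's contrasts".

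**The only printed formula** is `glm(case ~ cb.total_aedes + cb.ns1positive + ns(time, 3) + woy, family = quasipoisson, data)`. It belongs to a separate distributed-lag analysis (DLNM) that relates cases to NS1-positive mosquito pools. It has no arm term and no offset.

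**Exposure.** Under Methodology: "Eight apartments with 7979 residential units will be selected and randomised into intervention and control", and "Apartment will be the item of randomisation". Sizes per apartment are not listed, and no stratification or matching on size is described. Under Phase II: "A maximum of 21 traps will be set per apartment block, on every third floor". Control clusters have no traps.

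**Planned effect.** The sample size assumes a 2% yearly risk per housing unit, halved by the intervention. That is a quantity per unit, not a count.

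**The concern.** A trial sized on risk per unit should be analysed on cases per unit. Expected cases in an apartment are proportional to its number of units, and expected catch rises with the number of traps. If neither enters the model, a larger building looks like more dengue and a floor with more traps looks like more vectors.

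Two analyses are affected in different ways. In the comparison of arms, size variation adds noise between apartments, and with eight clusters a chance imbalance in units between arms carries over into the estimated count ratio. In the contrasts between blocks and floors, nothing is randomised with respect to size or trap number, so any difference in exposure is confounded with the quantity being compared.

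**Working it through.** **The plan's own figure.** There is no stated figure on this point. The nearest is 2855 units per arm. With p1 = 0.02, p2 = 0.01, two-sided alpha 0.05 and power 0.80:

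n = [1.960 × √(2 × 0.015 × 0.985) + 0.842 × √(0.02 × 0.98 + 0.01 × 0.99)]² / 0.01² = 2319 per arm.

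This does not reproduce 2855 unless an unstated inflation of about 20% is assumed (2319 × 1.2 = 2783; 2319 / 0.8 = 2899). The point here does not depend on that figure. What matters is that it is defined per housing unit.

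**Expected counts.** Mean size is 7979 / 8 = 997.4 units. At 2% a year over 18 months (3%), a control apartment expects 997.4 × 0.03 = 29.9 cases, or 29.9 / 78 = 0.38 a week, in direct proportion to its units.

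**What the documents show about inequality.** 7979 is not a multiple of 8, so sizes are not all identical, but apartments of 997 and 998 units would satisfy that. A trap maximum is compatible with equal numbers in blocks of equal height. The size CV is therefore an assumption, and the range has to include values near zero.

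**Arm comparison.** Simulation of eight apartments, 4 v 4, with 7979 units in total, lognormal sizes, gamma apartment rates with assumed CV 0.25, Poisson cases, and 3% v 1.5% over 18 months. The test is a t-test (6 df) on log counts or log rates per apartment, standing in for a GLMM with an apartment random intercept.

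| Size CV (assumed) | Power, counts | Power, rates | Arm unit totals differ ≥1.25-fold |
|---|---|---|---|
| 0.05 | 0.66 | 0.67 | 0% |
| 0.1 | 0.64 | 0.68 | 0.2% |
| 0.2 | 0.55 | 0.67 | 11% |
| 0.4 | 0.35 | 0.65 | 42% |
| 0.6 | 0.24 | 0.62 | 58% |

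These results carry simulation error of about 0.01. With no true effect, both versions reject in about 5% of runs at every size CV. At CV 0.6, about 9% of allocations differ 2-fold or more in units, which is as large as the planned effect.

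**If the model had no apartment random intercept** (plain Poisson, no other variation between apartments), type I error without the offset would be 18%, 40% and 55% at size CV 0.2, 0.4 and 0.6, against about 5% with it.

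**Contrasts.** Take two apartments with the same 3% risk over 18 months and Poisson variation only. The Tukey critical value for eight groups is 3.03.

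- 500 v 1500 units: 15 v 45 expected cases; z = ln 3 / √(1/15 + 1/45) = 3.68. Raw counts are declared different in 78% of simulated runs, against 0.2% with a log(units) offset.
- 800 v 1200 units: 24 v 36 expected cases; z = ln 1.5 / √(1/24 + 1/36) = 1.54. Rejection is 5.0% against 0.1%.

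The unit numbers in both examples are illustrative.

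**The case against.** **The plan is silent; it does not exclude an offset.** This stands for the GLMM. Its formula is not printed, so the charge is that the exposure term is unspecified. The formula that visibly lacks an offset is the DLNM. If that is fitted to one aggregated series with constant exposure, log(units) is absorbed by the intercept.

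**Inequality is not shown.** This also stands. A reader might infer from the indivisible total and the trap ceiling that apartments and trap numbers differ materially. The documents do not support that, and with nearly equal apartments the loss of power is negligible.

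**The test of the intervention would be invalid.** A reader might infer a biased or false-positive arm effect. In an apartment-level analysis type I error holds. The inflated rates above require a model without an apartment random effect. The plan names a mixed model, although it does not say which effects are random.

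**The trap offset would not touch the arm comparison.** Correct. Control clusters have no traps, so trap data can support comparisons only within the intervention arm. No intervention term is written for any model either, which is a larger gap within which the offset is one detail.

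**What remains.** The stated responses are counts, the stated contrasts are on numbers, and the planning quantity is per unit. Leaving the denominator open would also allow the choice to be made after the data are seen.

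**Conclusion.** The point holds as an unspecified exposure term, not as a demonstrated bias. For the arm comparison, the loss of power runs from about 1 point (size CV 0.05) through 12 points (0.2) to 38 points (0.6). This assumes lognormal sizes, a between-apartment rate CV of 0.25 and an apartment-level analysis, and none of the three is stated in the documents. The harm is lost precision and chance imbalance.

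The block and floor contrasts are the firmer part. Followed as written, they read more units as more dengue and more traps as more vectors wherever these numbers differ. How far they differ cannot be learned from the documents. The change should be made, because it is nearly free and removes the dependence on those unreported numbers.

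**What to change.** - **Cases:** print the GLMM formula, with an apartment random intercept and `offset(log(residential units))` at the level analysed (apartment, block or floor). Use the same offset in the contrasts.
- **Mosquitoes:** include `offset(log(traps retrieved that week))` in the GLMM and its block and floor contrasts, in intervention clusters only.
- **DLNM:** use mosquitoes per trap if the number of working traps varies by week, and add a units offset if apartments are stacked. It is redundant for one aggregated series with constant exposure.
- **Reporting:** give rate ratios per unit-week and per trap-week, and list units and traps for each apartment.

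The cost is one term per model. Units can be counted, and traps are already checked weekly. There is a small downside: an offset assumes that counts scale in proportion to units or traps. This can be checked by fitting log(exposure) as a covariate and seeing whether its coefficient is near 1. Floor-level case contrasts also need unit counts per floor, which would have to be collected.
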